5.1.1 Study Date Range and Duration

07/01/2021-06/30/2025

5.1.2 Number of Study Sites

1

5.2 Outcome Variables

Group differences in 1) [¹¹C]MRB-binding in brown adipose tissue (BAT), white adipose tissue (WAT), skeletal muscle, and norepinephrine-rich brain regions (hypothalamus and thalamus);

HIC 2000030749

and 2) microneurography (muscle sympathetic nerve activity (MSNA)). Correlations between NET in the brain and peripheral NET and MSNA.

5.2.1 Primary Outcome Variables

The primary objective of this study is to determine whether sympathetic nervous system (SNS) activity in adipose tissue (WAT and BAT), muscle and brain is altered in individuals with obesity in comparison to individuals with normal weight. Simultaneous multi-organ SNS activation will be obtained with a radiotracer for norepinephrine transporters (NET) for whole-body Positron Emission Tomography (PET) imaging and microneurography (gold standard test for assessment of muscle SNS activity).

Primary outcome: SNS activity measured by [¹¹C]MRB binding in adipose tissue, muscle and brain; and sympathetic burst in muscle (measured with microneurography).

5.2.2 Secondary Outcome Variables (if applicable)

The secondary objectives of this study are: 1) to evaluate whether gender differences affect peripheral SNS in healthy normal weight and obese men and women in adipose tissue (WAT and BAT) and muscle (resting/fasting); 2) To investigate the relationship between peripheral and central SNS activity in obesity, by correlating SNS activity in peripheral tissues (WAT, BAT, and muscle) and brain; and 3) To investigate NET CNS and peripheral SNS activity before and after a high carbohydrate mixed meal in lean and obese men and women.

5.2.3 Exploratory Outcome Variables (if applicable)

N/A

5.3 Study Population

The subjects we plan to enroll are in good medical health as evidenced by the medical history review during screening and lean (BMI 18.5-24.9 kg/m²) or non-diabetic obese (BMI 30-50 kg/m²).

5.3.1 Number of Participants

We plan to enroll 20 participants with normal BMI (10 women and 10 men) and 20 with obesity (10 women and 10 men).

5.3.2 Eligibility Criteria/Vulnerable Populations

Inclusion Criteria:

HIC 2000030749

In order to be eligible to participate in this study, an individual must meet all of the following criteria:

1. Provision of signed and dated informed consent form
2. Stated willingness to comply with all study procedures and availability for the duration of the study
3. Age 18–45 years
4. In good general health as evidenced by medical history and lean (BMI 18.5-24.9 kg/m²) or non-diabetic obese (BMI 30-50 kg/m²) with a fasting plasma glucose (FPG) <100 mg/dL and a hemoglobin A1c <5.7%.

Exclusion Criteria:

An individual who meets any of the following criteria will be excluded from participation in this study:

1. Hypertension
2. Cardiac or pulmonary disease
3. Known history of Type 1 or Type 2 diabetes
4. Hepatic disease, swallowing and gastrointestinal disorders, including but not limited to diverticulitis and inflammatory bowel disease
5. Disorders or impairment of the gag reflux
6. Subjects with previous gastrointestinal surgery.
7. Subjects with a pacemaker or other implanted electro medical device
8. Current use of anti-obesity medications, supplements and/or anti-hyperglycemic medications
9. Neurological injury or illness, and psychiatric medications
10. Women who are pregnant or lactating
11. Subjects who suffer from claustrophobia
12. Subjects who have received a diagnostic or therapeutic radiopharmaceutical within 7 days prior to participation in this study
13. Subjects who work with radiation or have participated in other research studies involving ionizing radiation within one year of the PET scans that would cause the subject to exceed the yearly dose limits.
14. Subjects with history of IV drug use which would prevent venous access for PET tracer injection
15. Severe motor problems that prevent the subject from lying still for PET and MR imaging
16. Subjects who complain of chronic pain
17. Blood donation within 8 weeks of the study
18. Non-English speaking subjects
19. Subjects with poor venous access
20. Subjects with an allergy or intolerance to the carbohydrate meal or IV contrast.
21. Subjects with a history of bleeding disorders

HIC 2000030749

- 22. Subjects on anticoagulation medications.
- 23. Subjects who are Transgender

6 Methods

6.1 Treatment

6.1.1 Identity of Investigational Product

[¹¹C]MRB will be prepared at the Yale PET Center under the supervision of Drs. [name] and [name] in accordance with local Chemistry Manufacturing & Control (CMC) procedures and quality specifications described in our local Drug Master File (DMF), which has been approved by the Yale University Radioactive Drug Research Committee (YU RDRC).

6.1.2 Dosage, Administration, Schedule

N/A

6.1.3 Method of Assignment/Randomization

Method of Assignment/Randomization- The order of the PET scan visits 2 (PET-CT Fasting) and 3 (PET/CT-MMT) will be randomly assigned (with a 50% chance of being assigned to each visit). SNSA visits 4 (fasting) and 5 (MMT) will be also be also be randomized (with a 50% chance of being assigned to each visit).

Blinding and Procedures for Unblinding

N/A

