4.3 Secondary Objectives (if applicable)

The secondary objectives of this study are: 1) to evaluate whether gender differences affect peripheral SNS in healthy normal weight and obese men and women in adipose tissue (WAT and BAT) and muscle (resting/fasting); 2) To investigate the relationship between peripheral and central SNS activity in obesity, by correlating SNS activity in peripheral tissues (WAT, BAT, and muscle) and brain; and 3) To investigate NET CNS and peripheral SNS activity before and after a high carbohydrate mixed meal in lean and obese men and women.

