High Carbohydrate Mixed meal test (MMT): Two weeks after visit 2, participants will come to the PET Center after a 10-hour overnight fast. A nurse will insert an intravenous (IV) catheter and subjects will ingest a liquid meal (65% CHO, 20% fat, and 15% protein, equal to 40% of daily energy expenditure, per ~16 ounces) to be prepared by the Metabolic Kitchen located at the HRU. Blood samples will be collected at -10, 0, 15, 30, 60, 90, and 120 min for measurement of glucose, insulin and C-peptide concentrations ⁷. Plasma samples will be drawn at baseline and throughout the MMT for measurement of additional hormones (such as leptin, ghrelin, thyroid hormones, and catecholamines) and free fatty acids (FFA) levels. Insulin and glucose will be used to calculate indexes of insulin sensitivity ⁷⁻⁹. Hormones, glucose and FFA will be correlated with PET measurements of brown fat at baseline and during the MMT. Approximately 60 mL of blood will be drawn at this visit.

HIC 2000030749

Participants will undergo whole body [¹¹C]MRB PET scan as described in visit 3. After the MMT, PET data will be acquired dynamically for 120 min using the Siemens mCT-X whole-body PET/CT scanner after an intravenous bolus dose of MRB (~20mCi).

The order of the PET scan visits 2 and 3 will be randomized.

PET and MSNA visits do not need to occur in sequence, i.e. PET scans can occur before or after the MSNA.

Measurement of Energy Intake: Hunger and fullness will be determined immediately before, during and after the PET scans with Visual Analog Scales (VAS).

Visit 4 – Sympathetic Nervous System Activity (SNSA) measurement Visit - Fasting

Two weeks after visit 3, participants will be asked to return for a separated visit for measurements of SNS activity at rest and fasting. This visit will be performed at the Pierce Laboratory ([name] laboratory). The participants will come in the morning (~9am) and will be asked to fast for 10-hour and to maintain their regular exercise routine. The following measurements will be obtained: MSNA, heart rate (HR), blood pressure (BP), electrocardiogram (EKG), and heart rate variability. The proposed procedures will be performed at fasting (baseline). Participants will be asked to maintain their regular exercise routine.

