6.4 Statistical Method

6.4.1 Statistical Design

Primary endpoints: Group differences in 1) [¹¹C]MRB-binding in brown adipose tissue (BAT), white adipose tissue (WAT), skeletal muscle, and norepinephrine-rich brain regions (hypothalamus and thalamus); and 2) microneurography (muscle sympathetic nerve activity (MSNA)). Correlations between NET in the brain and peripheral NET and MSNA.

Secondary endpoints: Plasma hormone levels, heart rate, blood pressure, electrocardiogram (beat-to-beat)..

Statistical Analysis: Before statistical testing, all continuous variables will be tested for normality of distribution. Summary statistics will be computed. For between-group comparisons of patient characteristics, two sample t-test or Mann-Whitney U test will be used for continuous variables, and Fisher's exact test for categorical variables. Comparisons of repeatedly measured MSNA will be made using the mixed model analysis. Fixed factors include group and sex and their interactions. Linear contrasts comparing differences between groups or different time points within a group will be estimated.

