6.5 Planned Analyses

6.5.1 Primary Objective Analysis

The primary objective of this study is to quantify sympathetic nervous system (SNS) activity by [¹¹C]MRB PET imaging and microneurography (MSNA). [¹¹C]MRB binding will be quantified in adipose tissue (WAT and BAT), muscle; and whether [¹¹C]MRB binding and sympathetic bursts are altered in individuals with obesity in comparison to individuals with normal weight.

Statistical Analysis: Before statistical testing, all continuous variables will be tested for normality of distribution. Summary statistics will be computed. For between-group comparisons of patient characteristics, two sample t-test or Mann-Whitney U test will be used for continuous variables, and Fisher's exact test for categorical variables. Comparisons of repeatedly measured MSNA will be made using the mixed model analysis. Fixed factors include group and sex and their interactions. Linear contrasts comparing differences between groups or different time points within a group will be estimated.

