6.5.9 Subsets and Covariates

N/A

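### The order of fasting and meal visits has no specified blocking and no period or sequence term in the model, so any visit-order effect adds avoidable error to the meal-response contrasts

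*Combined protocol and SAP*

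**What the plan says.** Section 6.1.3, repeated in section 5.1, holds the whole randomisation method. The order of PET visits 2 and 3 "will be randomly assigned (with a 50% chance of being assigned to each visit"), and separately "SNSA visits 4 (fasting) and 5 (MMT) will be also be also be randomized (with a 50% chance of being assigned to each visit"). Blocks, strata and the way the list is produced are not mentioned.

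Enrolment is fixed by BMI group and sex in section 5.3.1: "We plan to enroll 20 participants with normal BMI (10 women and 10 men) and 20 with obesity (10 women and 10 men"). That makes four cells of 10.

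The comparison that depends on visit order is secondary objective 3 in section 4.3: "To investigate NET CNS and peripheral SNS activity before and after a high carbohydrate mixed meal in lean and obese men and women". The two PET visits are two weeks apart (section 5.1: "Two weeks after visit 2, participants will come to the PET Center after a 10-hour overnight fast"), and so are the two SNSA visits.

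Sections 6.4.1 and 6.5.1 give one repeated-measures model, for MSNA: "Fixed factors include group and sex and their interactions". The next sentence reads "Linear contrasts comparing differences between groups or different time points within a group will be estimated". Period, sequence and visit condition are not among the named factors. No model is stated for the PET outcomes, and section 6.5.9, on subsets and covariates, is marked N/A.

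**The concern.** Each person is measured once fasting and once after the meal, so this part of the study is a two-period crossover in visit condition. If the second visit differs systematically from the first, a person seen fasting first shows the meal effect plus that shift, and a person seen meal first shows the meal effect minus it. The shift cancels only when the two orders are equally frequent, or when the model estimates it.

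The protocol gives reasons to expect some shift. Microneurography involves a nerve search of up to 60 minutes. Section 3.2.1 describes paresthesia lasting 2 to 10 days in some participants and rules out sampling a nerve site twice, so the second recording comes from a new site. Section 6.4.2 mentions technical difficulty in repeating the procedure in obese women.

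With 10 people per cell, unequal orders are easy to get by chance. What is at stake is the precision of the lean-versus-obese and male-versus-female meal responses in the one trial that will be run. Section 2.1.2 says that sex differences in the response to food will be examined, so cell-level comparisons are intended.

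**Working it through.** **The plan's own figures.** The plan gives no figure for order balance beyond the 50% chance. Its fasting sample size reproduces: d = (1.15 − 0.80)/√((0.19² + 0.12²)/2) = 2.20, and a two-sided t-test (alpha 0.05 assumed, since none is stated) has power 0.860 at 5 per group and 0.929 at 6. So 6 per group is right for 90%. That calculation concerns the fasting group difference and does not involve visit order.

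**Inputs.** Four cells of 10 and 20 per BMI group (section 5.3.1); 50% chance of each order, for two visit pairs (section 6.1.3). Assumption: simple, independent assignment, which the documents neither state nor exclude.

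**Chance imbalance** (exact binomial):

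| Event | Calculation | Probability |
|---|---|---|
| A given cell of 10 is exactly 5:5 | C(10,5)/2¹⁰ | 0.246 |
| A given cell is 7:3 or worse | 2 × P(Bin(10, 0.5) ≤ 3) | 0.344 |
| At least one of 4 cells is 7:3 or worse | 1 − 0.656⁴ | 0.815 |
| At least one of 8 cells (PET and SNSA) is 7:3 or worse | 1 − 0.656⁸ | 0.966 |
| A given BMI group of 20 is 13:7 or worse | 2 × P(Bin(20, 0.5) ≤ 7) | 0.263 |
| Order counts differ by 5 or more between two groups of 20 | exact | 0.154 |

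**Effect on the meal contrast.** Let δ be the second-minus-first-visit shift, assumed common to everyone. Within a set of n people, the error in the mean meal-minus-fasting difference is δ × (fasting-first count − meal-first count)/n. At 7:3 this is 0.4δ. Its expectation is zero and its SD is δ/√n: 0.32δ for a cell of 10 and 0.22δ for a group of 20. For a difference between two sets of n, the SD is 2√(2 × 0.25/n) × δ:
- lean versus obese, n = 20: 2√0.025 = 0.32δ
- one cell against another, n = 10: 2√0.05 = 0.45δ

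The primary fasting comparison is touched less. Fasting is the second visit for some people, so the group difference carries an error with SD √(2 × 0.25/20) = 0.16δ.

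**Type I error, simple assignment, no period term** (simulation, 20 people, δ in SDs of the within-person difference). The within-group meal test rejects at 0.051, 0.050 and 0.049 for δ = 0, 0.5 and 1. For the difference in meal response between two sets, with 20 or 10 in each, rates stay between 0.048 and 0.052. There is no inflation.

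**Blocking without a period term.** The within-group test falls to 0.028 at δ = 0.5 and 0.006 at δ = 1. The orders are balanced, but the unmodelled shift stays in the residual variance.

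**Period term without blocking.** The error is removed, at a variance cost of 1/(1 − b²), where b is the order difference divided by n: 4% at 6:4, 19% at 7:3 and 56% at 8:2 in a cell, and 10% at 13:7 in a group of 20.

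**Both together.** With blocks that close within each cell, every cell is 5:5, b = 0, and neither the error nor the variance cost remains, before dropout.

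**The case against.** The strongest reply is that this is a gap in description with little consequence. A blocked, stratified 1:1 list also gives each person a 50% chance, so the text does not rule blocking out. This stands: the imbalance probabilities hold only if assignment is simple.

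A reader might go further and infer that visit order is confounded with the meal response, or that false group-by-meal findings become more likely. The documents do not support that. Order is randomised, imbalance is chance with expectation zero, and the simulated error rate stays near 5%. Order coincides fully with condition in a given cell only at 10:0, which has probability 0.002. Nor is the 81% figure the chance of trouble in a given comparison; for a given BMI group, 13:7 or worse has probability 26%.

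Three further limits are fair. The listed factors are introduced by a word meaning that they are included, so the list may not be exhaustive, and it is given for MSNA only. The contrast affected is mainly a secondary objective. The two-week gap and the 60-minute control period before MSNA recording may keep the shift small. Blocking is also partly undone by loss: if each participant is lost independently with probability 10%, a 5:5 cell stays exactly balanced among completers about 46% of the time.

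What remains is that the stated model leaves a removable source of variation in the meal contrasts. Section 6.5.10 allows models to be adjusted as needed, but under missing data and without naming visit order.

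**Conclusion.** The point holds as a cheap gain in precision, not as a flaw that invalidates an analysis. No blocking or stratification is specified, and no period or sequence term is named. If assignment is simple, a first-to-second-visit shift adds error with SD 0.32 times the shift to the lean-versus-obese meal response, and 0.45 times between cells of 10. The absolute size is unknown because the documents give no estimate of the shift; if it is nil, nothing is lost. These figures assume a shift common to all participants and complete data. The contrasts are unbiased over randomisations and the type I error is not inflated. Severity is low: the main effect is on secondary objective 3, with a smaller one (0.16 times the shift) on the primary fasting comparison.

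**What to change.** 1. In sections 6.4.1 and 6.5.1, specify the mixed model for both MSNA and the PET outcomes with a random person effect and these fixed factors: group, sex, visit condition (fasting or meal), their interactions, period (first or second visit of the pair) and sequence. This also supplies the condition factor that the planned time-point contrasts need.
2. In section 6.1.3, state that the PET order and the SNSA order are each drawn from a prepared list of permuted blocks, stratified by BMI group and sex, with blocks that close within each cell of 10 so that each cell is 5:5 before dropout.
3. Adopt the two together. If only one is possible, choose the model terms: they remove the error whatever the split and still work after dropout, whereas blocking alone makes the test conservative.

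The cost is one prepared randomisation list and one or two degrees of freedom. No visit, procedure or sample size changes.

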6.1.4 Packaging/Labelling

N/A

6.1.5 Storage Conditions

N/A

6.1.6 Concomitant therapy

There are no restrictions.

6.1.7 Restrictions

There are no restrictions.

6.2 Assessments

Assessments are detailed in the figure below:

HIC 2000030749

Visit 1: Screening Visit
 
 -Review of Consent Form -Physical and Medical history review - Pregnancy Test (females) -EKG -Blood Work -OGTT -Body Composition -Tanita Scale -DXA Scan 	
Visit 2: Whole body PET/CT
 
Imaging
 
Fasting Visit
 
 - Urine Pregnancy Test (females) - Urine Drug Screen - [¹¹C]MRB - Low dose CT scan and PET scan - Norepinephrine levels (serum) 	
Visit 4: SNSA Visit – Fasting
 
 - BP, HR, PI, HR variability - EKG - MSNA
	
Visit 3: Whole body PET/CT
 
Imaging Mixed Meal Test Visit
 
 - [¹¹C]MRB - Urine Pregnancy Test (females) - Urine Drug Screen - Ingestion of mixed meal - Measurement of Energy Intake - Low dose CT scan and PET scan - Norepinephrine levels (serum) 	
Visit 5: SNSA Visit - Mixed Meal Test
 
 - Ingestion of mixed meal BP, HR, PI, HR variability - EKG - MSNA

Abbreviations: BP=blood pressure, EKG=electrocardiogram, HR=heart rate, MSNA=Muscle sympathetic nerve activity, SNSA=Sympathetic Nervous System Activity

Please note: The order of visits 2 and 3 are will be randomly assigned with a 50% chance of being assigned to each visit

6.2.1 Efficacy

See 5.1 General Design Description

6.2.2 Safety and Pregnancy-related policy

Risks Associated with Radiation:

No PET studies will be performed on pregnant or potentially pregnant women, as confirmed by pregnancy testing during evaluation and on each scan day before initiation of any scan procedures. If subjects are breastfeeding, they will not be able to participate in this research study.

6.2.3 Adverse Events Definition and Reporting

1. Personnel responsible for the safety review and its frequency:

The principal investigator, [name] [name] will be responsible for monitoring the data, assuring protocol compliance, and conducting the safety reviews at the specified frequency, which must be conducted at a minimum of every 6 months (including when reapproval of the protocol is sought). During the review process, the principal investigator will evaluate whether the study should continue unchanged, require modification/amendment, or close to enrollment. Either the principal investigator, the HIC, or the RSC have the authority to stop or suspend the study or require modifications.

HIC 2000030749

2. The risks associated with the current study are deemed greater than minimal for the following reasons: (choose those that apply)

The total amount of radiation in this study is from up to 3 low dose CT scans - used to optimize the PET scan – and up to 3 injections of radioactive material (20 mCi), [11C]MRB and from a low dose CT scans used to help obtain the PET images and the DXA scan .

The average yearly background radiation in the United States is about 0.3300 mrem. The amount of additional radiation from participating in this study is about 2.307 rem. This is equal to about 7.69 years worth of natural radiation.

The amount of radiation subjects will receive in this study is below the dose guidelines established by the RIDC guidelines for research purposes. This guideline sets an effective dose limit of 5 rem per year.

Adverse effects of the radiopharmaceuticals in this study have not been reported. However, the possibility exists for a rare reaction to any of the substances or procedures to which a subject is exposed.

3. Attribution of Adverse Events:

Adverse events will be monitored for each subject participating in the study and attributed to the study procedures / design by the principal investigator [name] [name], according to the following categories:

- a.) Definite: Adverse event is clearly related to investigational procedures(s)/agent(s).
- b.) Probable: Adverse event is likely related to investigational procedures(s)/agent(s).
- c.) Possible: Adverse event may be related to investigational procedures(s)/agent(s).
- d.) Unlikely: Adverse event is likely not to be related to the investigational procedures(s)/agent(s).
- e.) Unrelated: Adverse event is clearly not related to investigational procedures(s)/agent(s).

4. Plan for Grading Adverse Events:

HIC 2000030749

The following scale will be used in grading the severity of adverse events noted during the study:

1. Mild adverse event
2. Moderate adverse event
3. Severe

Plan for Determining Seriousness of Adverse Events:

Serious Adverse Events:

In addition to grading the adverse event, the PI will determine whether the adverse event meets the criteria for a Serious Adverse Event (SAE). An adverse event is considered serious if it results in any of the following outcomes:

1. Death.
2. A life-threatening experience in-patient hospitalization or prolongation of existing hospitalization.
3. A persistent or significant disability or incapacity.
4. A congenital anomaly or birth defect; OR
5. Any other adverse event that, based upon appropriate medical judgment, may jeopardize the subject's health and may require medical or surgical intervention to prevent one of the other outcomes listed in this definition.

An adverse event may be graded as severe but still not meet the criteria for a Serious Adverse Event. Similarly, an adverse event may be graded as moderate but still meet the criteria for an SAE. It is important for the PI to consider the grade of the event as well as its "seriousness" when determining whether reporting to the IRB is necessary.

6. Plan for reporting UPIRSOs (including Adverse Events) to the IRB

The principal investigator will report the following types of events to the IRB:

Any incident, experience or outcome that meets ALL 3 of the following criteria:

1. Is unexpected (in terms of nature, specificity, severity, or frequency) given (a) the research procedures described in the protocol-related documents, such as the IRB-approved protocol and informed consent document and (b) the characteristics of the subject population being studied; AND

HIC 2000030749

2. Is related or possibly related to participation in the research (possibly related means there is a reasonable possibility that the incident, experience, or outcome may have been caused by the procedures involved in the research); AND
3. Suggests that the research places subjects or others at greater risk of harm (including physical, psychological, economic, legal, or social harm) than was previously known or recognized.

Unanticipated Problems Involving Risks to Subjects or Others (UPIRSOs) may be medical or non-medical in nature, and include – but are not limited to – serious, unexpected, and related adverse events and unanticipated adverse device effects. Please note that adverse events are reportable to the IRB as UPIRSOs only if they meet all 3 criteria listed above.

These UPIRSOs/SAEs will be reported to the IRB in accordance with IRB Policy 710, using the appropriate forms found on the website. All related events involving risk but not meeting the prompt reporting requirements described in IRB Policy 710 should be reported to the IRB in summary form at the time of continuing review. If appropriate, such summary may be a simple brief statement that events have occurred at the expected frequency and level of severity as previously documented. In lieu of a summary of external events, a current DSMB report can be submitted for research studies that are subject to oversight by a DSMB (or other monitoring entity that is monitoring the study on behalf of an industry sponsor).

7. Plan for reporting adverse events to co-investigators on the study, as appropriate the protocol's research monitor(s), e.g., industrial sponsor, Yale Cancer Center Data and Safety Monitoring Committee (DSMC), Protocol Review Committee (PRC), DSMBs, study sponsors, funding and regulatory agencies, and regulatory and decision-making bodies.

For the current study, the following individuals, funding, and/or regulatory agencies will be notified:

- All Co-Investigators listed on the protocol.
- National Institute of Health

1 Other Data Safety Monitoring Board (DSMB) or Committee (DSMC): The Yale PET Center's internal Data Safety Monitoring Board, composed of the Directors of the PET Center, also meets to review any adverse events on a monthly basis.

1 Yale New-Haven Radiation Safety Committee (if applicable)

Yale University Radiation Safety Committee (if applicable)

The principal investigator [name] [name] will conduct a review of all adverse events upon completion of every study subject. The principal investigator will evaluate the frequency

HIC 2000030749

and severity of the adverse events and determine if modifications to the protocol or consent form are required.

Research staff will call subject 1-3 days after the PET scan to check in and address any adverse events that may have arisen post PET scan.

The study will be stopped if either of the following occur:

- 1) If 1 or more subjects experiences a serious adverse event (SAE), which is considered by the investigator to be possibly or probably related to the radiotracer.
- 2) If 2 or more subjects experience AEs of severe intensity, which are considered by the investigator to be possibly or probably related to the radiotracer and of clinical concern.

After review of the safety data, SAEs and AEs confirmed to have been related to the radiotracer will be reported to the FDA and the appropriate regulatory committees at Yale. The study will be placed on hold until a determination is made as to whether the study may continue as written, if modifications are needed, or if the study will be discontinued.

Definitions

Adverse event (AE) means any untoward medical occurrence associated with the use of an intervention in humans, whether or not considered intervention-related (21 CFR 312.32 (a)).

An AE or suspected adverse reaction is considered "serious" (SAE) if, in the view of either the investigator or sponsor, it results in any of the following outcomes:

- death,
- a life-threatening adverse event,
- inpatient hospitalization or prolongation of existing hospitalization,
- a persistent or significant incapacity or substantial disruption of the ability to conduct normal life functions,
- a congenital anomaly/birth defect, or
- An important medical event that may not result in death, be life-threatening, or require hospitalization may be considered serious when, based upon appropriate medical judgment, they may jeopardize the participant and may require medical or surgical intervention to prevent one of the outcomes listed in this definition. Examples of such medical events include allergic bronchospasm requiring intensive treatment in an emergency room or at home, blood dyscrasias or convulsions that do not result in inpatient hospitalization, or the development of drug dependency or drug abuse.

HIC 2000030749

Severity

Adverse events will be graded according to [name grading scale, e.g. CTCAE v5.0]. For AEs not included in the protocol defined grading system, the following guidelines will be used to describe severity.

- Mild – Events require minimal or no treatment and do not interfere with the participant's daily activities.
- Moderate – Events result in a low level of inconvenience or concern with the therapeutic measures. Moderate events may cause some interference with functioning.
- Severe – Events interrupt a participant's usual daily activity and may require systemic drug therapy or other treatment. Severe events are usually potentially life-threatening or incapacitating. Of note, the term "severe" does not necessarily equate to "serious".]

Relationship to Investigational Product

All AEs must have their relationship to study intervention assessed by the clinician who examines and evaluates the participant based on temporal relationship and his/her clinical judgment. The degree of certainty about causality will be graded using the categories below. In a clinical trial, the study product must always be suspect.

- Definitely Related – There is clear evidence to suggest a causal relationship, and other possible contributing factors can be ruled out. The clinical event, including an abnormal laboratory test result, occurs in a plausible time relationship to study intervention administration and cannot be explained by concurrent disease or other drugs or chemicals. The response to withdrawal of the study intervention (dechallenge) should be clinically plausible. The event must be pharmacologically or phenomenologically definitive, with use of a satisfactory rechallenge procedure if necessary.
- Probably Related – There is evidence to suggest a causal relationship, and the influence of other factors is unlikely. The clinical event, including an abnormal laboratory test result, occurs within a reasonable time after administration of the study intervention, is unlikely to be attributed to concurrent disease or other drugs or chemicals, and follows a clinically reasonable response on withdrawal (dechallenge). Rechallenge information is not required to fulfill this definition.
- Potentially Related – There is some evidence to suggest a causal relationship (e.g., the event occurred within a reasonable time after administration of the trial medication). However, other factors may have contributed to the event (e.g., the participant's clinical condition, other concomitant events). Although an AE may rate only as "possibly related" soon after discovery, it can be flagged as requiring more information and later be upgraded to "probably related" or "definitely related", as appropriate.

HIC 2000030749

- Unlikely to be related – A clinical event, including an abnormal laboratory test result, whose temporal relationship to study intervention administration makes a causal relationship improbable (e.g., the event did not occur within a reasonable time after administration of the study intervention) and in which other drugs or chemicals or underlying disease provides plausible explanations (e.g., the participant's clinical condition, other concomitant treatments).
- Not Related – The AE is completely independent of study intervention administration, and/or evidence exists that the event is definitely related to another etiology. There must be an alternative, definitive etiology documented by the clinician.

Expectedness

The Principal Investigator will be responsible for determining whether an AE is expected or unexpected. An AE will be considered unexpected if the nature, severity, or frequency of the event is not consistent with the risk information previously described for the study intervention.

